Vericiguat stimulates sGC both independently of, and synergistically with, NO¹⁵. Vericiguat enhances the cGMP pathways by directly stimulating sGC through a binding site independent of NO, and it sensitizes sGC to any bioavailable NO by stabilizing NO binding to the sGC binding site¹⁵. Thus, the beneficial attributes of NO bioavailability may accrue despite the decreased bioavailability associated with the metabolic syndrome. Our study will test whether the coronary vascular response to isometric handgrip exercise (IHE), an endothelial-dependent stressor, improves from the study performed prior to and that performed following the administration of vericiguat. We will also test whether the response differs from the response in those randomized to placebo and whether the results on the follow-up exams differ between those randomized to vericiguat and those randomized to placebo.

If successful, a sGC mediated prevention strategy could be tested to learn whether improved coronary vascular function would improve outcomes in those with, and at risk for, the development and progression of coronary vascular disease (Figure 1).

[figure not shown]

Figure 1: Hypothesis: Vericiguat improves coronary vascular endothelial function in patients with the metabolic syndrome or type 2 diabetes mellitus and impaired coronary vascular function. L-Arg= L-arginine, NO= nitric oxide, eNOS= endothelial nitric oxide synthase, sGC= soluble guanylyl cyclase, cGMP= cyclic guanosine monophosphate, PKG= cyclic GMP-dependent protein kinases

We have extensive experience using magnetic resonance imaging (MRI) to assess coronary endothelial-dependent vascular function non-invasively in healthy individuals and in those with coronary disease¹¹ and pro-inflammatory states¹⁰ using isometric handgrip exercise, an endothelial NO pathway-specific stressor⁹

Our MRI technique can detect meaningful changes in coronary vascular function in people with impaired baseline coronary vascular function following an intervention and we will use this methodology in the proposed study to assess the impact of stimulating sGC with vericiguat on coronary vascular function in patients with impaired baseline function.

4. Study Procedures

a. *Study design, including the sequence and timing of study procedures (distinguish research procedures from those that are part of routine care).*

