Participants who meet enrollment criteria will be asked to provide consent. Women of reproductive capacity will undergo a urine pregnancy test and those who are pregnant will be excluded from further participation. Men over 40 years of age and women over 50 years of age with no clinical coronary angiographic study within the prior 36 months demonstrating no significant coronary disease in at least one major coronary artery will undergo a research CT scan to measure coronary calcium score. If the score is ≤ 10 in at least one major coronary artery, they, and those who meet the other eligibility criteria will undergo assessment of coronary vascular function using MRI methodology. Those with normal function will not undergo any additional study

Date: June 3, 2025

Principal Investigator: [name]., PhD.

Application Number: IRB00310207

procedures. Those with abnormal global (micro- and macro- vascular function) coronary vascular function will undergo an echocardiographic study to assess systolic and diastolic function and baseline laboratory studies. They will then be randomized to vericiguat or placebo in a 2:1 ratio. Following randomization, the participants will undergo a study drug titration phase as follows: Initial 2.5 mg/day for two weeks, then 5 mg/day for two weeks, and then 10 mg/day for two weeks. Blood pressure and clinical symptoms will be assessed following each two-week period to determine whether the up titration should be performed, as guided by evaluation of blood pressure and clinical symptoms²¹. Identical appearing placebo tablets will also be titrated so as to maintain double-blinding of the investigators and participants. Next, study participants will continue the maximally tolerated maintenance dose for an additional 6 weeks. The study concludes with a final assessment of global (micro- and macro- vascular function) coronary vascular function with the same MRI protocol and follow-up laboratory studies and an echocardiogram. (Figure 2)

[figure not shown]

Figure 2: Study overview: Vericiguat in Patients with Metabolic Syndrome or type 2 diabetes mellitus and Coronary Vascular Dysfunction.

Study type: Interventional-treatment

Trial design: Randomized

Number of Enrolled Participants: 45 total participants, 30 in the vericiguat and 15 in the placebo group.

Coronary Artery Calcium (CAC) Score

Date: June 3, 2025

Principal Investigator: [name]., PhD.

Application Number: IRB00310207

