For men >40 and women >50 years of age who have not had coronary angiography (including CT angiography) within the prior 36 months, a CAC score will be determined. A computed tomography (CT) scan will be performed without contrast agents with 10 to 15 minutes of total room time at about 1 to 2.5 mSv of radiation²².

MRI methods for Coronary Vasoreactivity:

MR will be performed on a 3 T CMR scanner (Achieva, Philips Healthcare, Best, NL) in the morning after an overnight fast. For endothelial function imaging, alternating anatomical and velocity-encoded images will be collected at baseline and during approximately 6 min of continuous isometric handgrip exercise (IHE). The exercise is performed using a handgrip dynamometer at 30% of each participant's maximum force, which is determined prior to the MRI study, as previously reported^{9,23}. Images will be taken perpendicular to a proximal or mid-straight segment of the coronary artery and/or coronary sinus best identified on survey scans¹¹. Cross-sectional anatomical (bright blood sequence) and phase contrast velocity encoded spiral CMR will be obtained using single breath-hold cine sequences with reproducibility of the techniques published previously^{9,23}. The MRI will be used to measure cross-sectional area (CSA), coronary flow velocity (CFV), and to calculate coronary blood flow (CBF) changes in response to the IHE. If technical problems prevent adequate interrogation of the coronary response, the participant will be asked to undergo a second screening MRI study. Coronary MRI will be repeated following the study drug administration period with an identical protocol with special attention taken to interrogate the same coronary segments as those studied at baseline, using anatomic landmarks of coronary ostia and branch vessels- as we have done in the past⁹ and to replicate the identical MRI IHE protocol.

MRI analysis:

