 - fasting high-density lipoprotein (HDL) cholesterol level < 40 mg/dL in men or < 50 mg/dL in women
 - fasting blood glucose > 100 mg/dL or HbA1c $\geq 5.7\%$
- Either one of the following:
 - Men ≤ 40 or women ≤ 50 years of age with no history or symptoms of ischemic heart disease, or
 - Men >40 or women >50 years of age with either one of the following:
 - a coronary angiography (including CT angiography) within the past 36 months showing no significant coronary artery disease in at least one major coronary artery, defined as $>50\%$ stenosis of the left main coronary artery and/or $>70\%$ stenosis of another major coronary vessel, or
 - a coronary artery calcium score obtained within the prior 36 months or if no prior calcium scan, one performed as a research study following consent with a score ≤ 10 in at least one major coronary artery.
- IHE-induced %-change in coronary flow < or equal to 13%

Exclusion Criteria:

- Systolic blood pressure <110 mm Hg
- Current or anticipated use of long-acting nitrates, a sGC stimulator, or phosphodiesterase type 5 (PDE5) inhibitors
- Hematocrit $<30\%$
- Unable to understand the risks, benefits, and alternatives of participation so as to provide informed consent
- Women who are pregnant.
- Women who are breastfeeding
- Women with reproductive capacity not using an acceptable form of contraception
- History of claustrophobia
- Inability to lie flat and still for 45 minutes

- Presence of non-MR-compatible objects or devices, such as intra-orbital debris, intra-auricular implants, intra-cranial clips, an implanted defibrillator or a pacemaker
- History as a machinist, welder, metal worker or a similar activity that poses the risk of metal exposure to the eyes

6. Drugs/ Substances/ Devices

a. *The rationale for choosing the drug and dose or for choosing the device to be used.*

As detailed above, we propose using vericiguat to “bypass” the requirement for nitric oxide synthesis in an attempt to improve endothelial function and hence coronary vascular function in individuals with preexisting dysfunction²⁷. If successful, a sGC-directed prevention strategy may improve coronary vascular function and decrease cardiovascular risk. The dose and titration described to reach the dose is that used for patients with heart failure and approved by the FDA to treat those patients²⁸.

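### The only pregnancy test described comes before the screening MRI, and the visible text sets no limit on its age when study drug starts

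*Combined protocol and SAP*

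**What the plan says.** Section 4a, whose template heading asks for the design "including the sequence and timing of study procedures", sets out the steps in order. After consent comes the pregnancy test: "Women of reproductive capacity will undergo a urine pregnancy test and those who are pregnant will be excluded from further participation". A research CT for calcium scoring follows for some older participants, and then the screening MRI.

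The MRI result decides who continues. Of participants with a normal result, section 4a says: "Those with normal function will not undergo any additional study" procedures. Those with abnormal function "will undergo an echocardiographic study to assess systolic and diastolic function and baseline laboratory studies". Only after that: "They will then be randomized to vericiguat or placebo in a 2:1 ratio". Section 5 makes the MRI value an entry criterion: "IHE-induced %-change in coronary flow < or equal to 13" per cent. If a scan is technically inadequate, "the participant will be asked to undergo a second screening MRI study" (section 4a, MRI methods).

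Section 7c allows two months for analysing each MRI and 48 hours for the routine safety laboratory tests.

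Section 5 excludes pregnant women, breastfeeding women and "Women with reproductive capacity not using an acceptable form of contraception". It attaches no test date or window to any of these. Section 8b adds a history and physical examination at baseline and at later visits, and names no pregnancy test.

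**The concern.** The test is at the start of screening and the first dose is at the end, with a result-dependent step between them. A woman who conceives during screening, or who was tested too soon after conception for a urine test to detect it, could meet every written requirement and begin 12 weeks of study drug while pregnant. The trial means to exclude pregnancy, and its contraception rule shows that it also means to prevent pregnancy after enrolment. Yet the visible text does not ask for a current negative result at the point where drug exposure begins.

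What is at stake is the safety of the few women to whom this applies. The comparison of treatment groups, the error rate and the power are not involved.

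**Working it through.** The plan states no figure for the age of the test at first dose, so there is nothing to reproduce. The check is to follow the written sequence and see which intervals have a limit.

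Gap from test to first dose = A + B + C + D, where:

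| Interval | Source | Stated limit |
|---|---|---|
| A: pregnancy test to screening MRI | 4a | none |
| B: MRI to its reading | 7c | two months per scan |
| C: reading to completed echocardiogram and baseline laboratory work | 4a, 7c | none overall; 48 hours for analysing safety samples once drawn |
| D: completion of C to randomisation and first dose | 4a | none |

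B cannot be skipped, because the flow response is an entry criterion (section 5). The value comes from images processed in semi-automated software (section 4a, MRI analysis), so it need not be known when the participant leaves the scanner. The limit in section 7c applies to every MRI, which includes the screening scan.

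Illustrations:

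1. *Everything on one day.* A = B = C = D = 0, so the gap is 0 days. Nothing in the text forbids this, and the consent test is then current.
2. *One scan read at its limit, all else immediate (assumption).* 0 + 2 months + 0 + 0 = 2 months.
3. *Repeat scan, each reading at its limit, all else immediate (assumption, including that the technical failure emerges only at reading).* 2 + 2 = 4 months.

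The third case shows that two months limits one reading and not the whole gap. A and D have no stated limit and C has none overall, so no upper end can be calculated. The written plan supports only this: the gap may be zero, one permitted step alone may take up to two months, and the total is not bounded.

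Dosing after that point lasts 2 + 2 + 2 weeks of titration plus 6 weeks of maintenance = 12 weeks (section 4a).

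The remaining safeguards, set beside the gap:

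- *Pregnancy exclusion (section 5).* It has no time limit, so a woman known to be pregnant before randomisation is ineligible. It does not say how pregnancy would become known after the consent test.
- *Contraception exclusion (section 5).* It makes conception during screening unlikely, but contraception can fail or not be used.
- *Baseline history and examination (section 8b).* These may raise a suspicion but can miss an early pregnancy.

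None of the three establishes status on the day drug starts.

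**The case against.** The strongest reply is that screening is probably short. The two-month figure sits among data-handling statements in section 7c and is an outer limit for analysis, not a screening timetable. Section 4c gives four to eight visits per participant. With four visits, the final visit leaves 4 − 1 = 3 for the titration checks and everything before drug, so screening must be compressed. This stands for the lower end. At the upper end, taking three titration checks and one or two final visits (MRI and echocardiogram together or apart), 8 − 3 − 1 = 4 or 8 − 3 − 2 = 3 visits remain before or at first dispensing. The protocol therefore allows screening over several days, and the visit count says nothing about the time between visits.

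A second reply is that absence cannot be fully confirmed. Figure 2 is the study overview and is not available here, and the consent pages were removed. A test window or a retest could appear in either. This also stands, and it is why the point is limited to the visible text.

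Third, few women may be affected. The trial has 45 participants aged 35 to 85, the number of reproductive capacity is not given, and those women must already be using contraception. This stands and bears on severity.

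A reader might infer that the test will typically be two months old, or that two months is the worst case. The documents support neither: the figure is a permitted maximum for one reading, and other intervals are open. A reader might also infer that the drug carries a known fetal hazard that the protocol ignores. The risk text in section 8a describes none, and it is an inference that the pregnancy exclusion is aimed at drug exposure.

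**Conclusion.** The point holds as a cheap improvement of minor severity. In the visible text, one urine pregnancy test is described, before the screening CT and MRI, with no maximum age at first dose and no retest before drug starts. The size of the gap cannot be stated beyond the range of possibilities: zero with same-day screening, up to two months from one MRI reading alone, and longer if other steps take time.

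This rests on reading the narrative in section 4a as the actual sequence, which its heading supports, and on nothing contrary appearing in Figure 2 or the consent pages. Site staff may already retest in practice, but the available text does not require it.

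It would go too far to read this as a threat to the trial's conclusions. It concerns participant safety only.

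**What to change.** In sections 4a and 5, require a negative urine pregnancy test for women of reproductive capacity on the day study drug is first dispensed, before randomisation. Let the consent test count if it was done that same day. Urine collection is already planned (section 2, secondary objective 3), so a baseline sample taken that day could be used.

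Testing before randomisation means that a positive result removes a woman before allocation, so no one is randomised and then withheld from treatment for this reason. This presumes that randomisation and first dispensing fall on the same day.

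The cost is one dipstick per eligible woman and a short amendment. That no extra visit is needed is an assumption: the protocol does not describe how drug is first dispensed, and remote dispensing would need a visit or another arrangement. The change has two limits. A same-day urine test can still miss a very early pregnancy, and it does not cover conception during the 12 weeks of dosing.

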Images will be analyzed blinded to study-drug assignment and clinical information for CEF (e.g., change in cross-sectional area (CSA), coronary flow velocity (CFV), and calculated coronary blood flow (CBF), as previously validated and described^{9,23}. Coronary CSA will be quantified using a semi-automated software tool (Cine version 3.15.17, General Electric, Milwaukee, WI, USA) as previously reported¹¹. For CBV and CBF measurements, phase-contrast images will be analyzed using semi-automated commercial software (FLOW Version 3.0, Medis, NL); the coronary blood-flow (CBF, in ml/minute) is derived from diastolic coronary flow velocity (CFV, in cm/sec) as previously described^{9,11}. Only native coronary segments will be analyzed. Our prior studies using this methodology demonstrated low intra- and inter-observer variability with good reproducibility over eight weeks⁹.

Echocardiography

Participants may also be asked to undergo echocardiographic studies to evaluate cardiac function. Systolic function will be assessed by measuring the ejection fraction (EF), calculated as stroke volume divided by the end-diastolic volume. Diastolic function will be assessed by looking at the annular e' velocity, the septal and lateral e' velocities, the average E/e' ratio, the LA volume index and the peak TR velocity²⁴. We will obtain images before and after a 90 second passive leg raise as well to assess hemodynamic variations²⁵. Strain and strain rate measurements will be obtained

using myocardial speckle tracking to evaluate regional myocardial contractile function²⁶.

b. *If your study involves data/biospecimens from participants enrolled under other research studies with a written consent or under a waiver of consent, please list the IRB application numbers for those studies. Please note: Certificate of Confidentiality (CoC) protections applied to the data in source studies funded by NIH or CDC will extend to this new study if the funding was active in 2016. If this situation applies, Section 36, question 6 in the application will need to be answered "Yes" and "Hopkins Faculty" should be selected in question 7. No other documents are required.*

Not applicable

c. *Study duration and number of study visits required of research participants.*

Study Duration: 24 months

Number of study visits per participant: 4 to 8, depending on whether the MRI and echo will be performed on the same day and how many titration steps are performed.

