d. *Blinding, including justification for blinding or not blinding the trial, if applicable.*

This study will be double-blinded to minimize bias and maximize the validity of the results. All study personnel and the participants will be blinded to study drug assignment to avoid bias in data collection and analysis. The Hopkins Investigational Pharmacy will have access to study drug assignment if there is a clinical need for the subjects' treating physicians to be aware of assignment.

e. *Justification of why participants will not receive routine care or will have current therapy stopped.*

Participants will continue to receive routine care and will not have any current therapy stopped.

f. *Justification for inclusion of a placebo or non-treatment group.*

This study is intended to develop an intervention and does not require participants to forgo treatment they would otherwise receive. Vericiguat is not considered a treatment for this patient population so the placebo group is not considered a "non-treatment" group.

g. *Definition of treatment failure or participant removal criteria.*

There is no defined treatment failure.

Participation in this study is on a volunteer basis. As such, individuals may decline continued participation. If new data appear indicating risks not presently foreseen associated with administration of the study drug or any of the study procedures, the study may be terminated and participants removed.

h. *Description of what happens to participants receiving therapy when study ends or if a participant's participation in the study ends prematurely.*

The study drug is not considered a treatment and thus will no longer receive the drug when the study ends or if participation ends prematurely.

i. *If biological materials are involved, please describe all the experimental procedures and analyses in which they will be used.*

The experimental procedure is venipuncture. Analyses for routine chemistry and hematology studies as well as markers/mediators of inflammation and the nitric oxide signaling pathway will be performed.

5. Inclusion/Exclusion Criteria

Inclusion Criteria:

- Age range 35-85 years
- Presence of type 2 diabetes mellitus or of the metabolic syndrome defined by the NCEP ATP III definition, with at least three of the following five criteria:
 - waist circumference > 40 inches (men) or > 35 inches (women)
 - blood pressure > 130/85 mmHg
 - fasting triglyceride (TG) level > 150 mg/dL

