b. *Justification and safety information if FDA approved drugs will be administered for non-FDA approved indications or if doses or routes of administration or participant populations are changed.*

Vericiguat is approved for reducing the risk of cardiovascular death and heart failure hospitalization following hospitalization or need for outpatient intravenous diuretics in adults with symptomatic chronic heart failure and ejection fraction less than 45%. The dose and route of administration are the same as that administered for this FDA approved indication. The dose is not changed from that used for the marketed drug.

c. *Justification and safety information if non-FDA approved drugs without an IND will be administered.*

We will be using an FDA approved drug.

7. Study Statistics

a. *Primary outcome variable.*

In a paired analysis, we hypothesize that there is a significant change in coronary flow and dimension with isometric handgrip exercise (IHE) in the group randomized to vericiguat from that measured at baseline, prior to the initiation of vericiguat, to that measured following vericiguat administration and up-titration. We will be using either a paired student t-test or a Wilcoxon test to examine this hypothesis.

In unpaired analyses, we hypothesize that the change in the vericiguat group from baseline to post-up titration will be greater than the change in the placebo group. We will be using either an unpaired student t-test or a Mann-Whitney test to examine this hypothesis

b. *Secondary outcome variables.*

We will conduct bivariate analyses to compare markers/mediators of inflammation and that of the nitric oxide pathway.

Other exploratory outcome variable that we are interested in include age, sex, and race. We will be using parametric and non-parametric tests for continuous variables and chi-square or Fisher's exact tests for categorical variables.

c. *Statistical plan including sample size justification and interim data analysis.*

Date: June 3, 2025

Principal Investigator: [name]., PhD.

Application Number: IRB00310207

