All sample size calculations are based on 80% power and 5% alpha error for two-sided tests. We have prior studies with small sample sizes to inform our baseline expectations¹². For our primary analysis, our minimum expected difference in change in coronary flow with IHE in the vericiguat group with our planned sample size of n=30 in the vericiguat group, allowing for 10% loss to follow-up at 8 weeks (n=27 remaining), with 80% power and an alpha of 0.05 is $7.8\% \pm 13.6\%$. The detectable effect size at 90% power is $9.1\% \pm 13.6\%$. (Figure 3).

[figure not shown]

Figure 3: Power and sample size calculated for estimated difference in change in coronary flow with IHE from baseline to 8 weeks in the vericiguat group

The study investigators will be responsible for analyzing the study data to assess the completeness of data collection, to assess any adverse events, and to identify any findings which may have clinical relevance. This will be performed while maintaining the blind. A Data Safety and Monitoring Committee will review and, if necessary unblind, the data when the outcomes of the first third (n=15) of the anticipated enrolled participants are available and at the end of the study. This committee may request to review/audit the data at any time.

The data will be maintained in a REDCap database.

The data will be unblinded following the completion of the protocol, and medical/scientific review has been completed, protocol violators have been identified and data has been declared complete, although the Hopkins Institutional Review Board and Data Safety and Monitoring Committee may request prior unblinding.

Date: June 3, 2025

Principal Investigator: [name]., PhD.

Application Number: IRB00310207

The routine safety laboratory studies will be analyzed within 48 hours of collection.
The MRI data will be analyzed within two months of each study

d. Early stopping rules.

The study will be stopped early on the recommendation of the Data Safety and Monitoring Committee or if there is any new published information regarding the safety of the study drug or the study procedures.

8. Risks

a. Medical risks, listing all procedures, their major and minor risks and expected frequency.

Study Drug:

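### MRI reading is not masked to visit and the eligibility read doubles as baseline, which exposes the paired test that sizes the trial

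*Combined protocol and SAP*

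**What the plan says.** **Masking.** Section 4a (MRI analysis) says "Images will be analyzed blinded to study-drug assignment and clinical information". Section 4d adds "All study personnel and the participants will be blinded to study drug assignment to avoid bias in data collection and analysis". Neither mentions visit, scan date or reading order, and no section plans a pooled or repeated read.

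**Timing of the reads.** Inclusion (section 5) requires "IHE-induced %-change in coronary flow < or equal to 13" per cent, so the baseline response must be quantified before randomisation. Section 7c says "The MRI data will be analyzed within two months of each study". In section 4a the follow-up scan comes after 6 weeks of titration and 6 weeks of maintenance. Section 7c speaks of 8 weeks, and the two intervals must be reconciled.

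**Human input.** Section 4a says "Coronary CSA will be quantified using a semi-automated software tool", and flow is also measured with semi-automated software.

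**Tests.** Section 7a lists two hypotheses under the primary outcome. The first is a before-after change within the vericiguat arm: "We will be using either a paired student t-test or a Wilcoxon test to examine this hypothesis". The second is unpaired: "we hypothesize that the change in the vericiguat group from baseline to post-up titration will be greater than the change in the placebo group". Section 7c sizes the primary analysis on the vericiguat arm alone.

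**The concern.** Masking to drug protects a comparison between arms. It does not protect a comparison of before with after inside one arm. If readings at follow-up run systematically higher than at baseline for any reason connected with the visit, the paired test counts the difference as improvement.

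The plan's reading sequence leaves room for this. The eligibility read is by nature a baseline read, and its result decides whether the participant can be randomised. On the stated timetable it is made before there is a follow-up scan to pair it with.

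The same read then appears to serve as the analysis baseline, since no other is planned. A participant whose reading fell at or below 13% partly through error will tend to read higher next time without any treatment. Both mechanisms push the paired estimate in the direction of benefit.

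**Working it through.** **1. The plan's own figure.** Inputs from section 7c: 30 × 0.9 = 27 analysed, SD of the paired change 13.6, two-sided alpha 0.05.
- Standard error = 13.6/√27 = 2.617; critical t on 26 df = 2.056.
- Power from the noncentral t with noncentrality d/2.617: 81.8% at d = 7.8 (stated 80%) and 91.7% at d = 9.1 (stated 90%).

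The stated figures reproduce and are slightly conservative. An observed mean change of 2.056 × 2.617 = 5.4 points is enough for p < 0.05.

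**2. Effect of a reading shift on the paired test.** Suppose there is no drug effect and follow-up responses are read b points higher on average. The noncentrality is b/2.617. The values of b are assumptions.

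| Assumed shift b (points) | Noncentrality | Two-sided rejection rate |
|---|---|---|
| 0 | 0 | 5.0% |
| 1 | 0.38 | 6.6% |
| 2 | 0.76 | 11.4% |
| 3 | 1.15 | 19.7% |
| 5 | 1.91 | 45.2% |

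**3. The same shift in the unpaired test.** With 2:1 allocation, placebo has 15 participants, and 15 × 0.9 = 13.5, so 13 or 14 analysed. A shift common to both arms cancels in the difference. Simulated rejection rates (27 versus 14, 40,000 runs) were 5.1% at b = 3 and 5.0% at b = 5. The price is power: with SD 13.6 assumed in both arms, power at 7.8 points is about 38% to 40%, and the difference detectable with 80% power is about 12.9 to 13.2.

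**4. Regression to the mean from selecting at 13%.** Assume normal responses with true mean 10 and true between-person SD τ. Within-person variance has a reading part r² and a scan-to-scan part s². For S² = τ² + s² + r² and a = (13 − 10)/S, the expected spurious change after selection is (s² + r²)/S × φ(a)/Φ(a). After re-reading the same baseline scan, s²/S × φ(a)/Φ(a) remains. To match the plan's SD of change, 2(s² + r²) = 13.6², so s² + r² = 92.48.

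| Assumed τ, r | s² | S | φ(a)/Φ(a) | Selecting read as baseline | After re-read |
|---|---|---|---|---|---|
| 10, 5 | 67.48 | 13.87 | 0.666 | 4.4 points | 3.2 points |
| 12, 7 | 43.48 | 15.38 | 0.678 | 4.1 points | 1.9 points |

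The re-read therefore removes about 1.2 and 2.2 points. If reading error were the only within-person variation (s = 0), the spurious change would be 1.4 and 2.3 points and a re-read would remove all of it. But the SD of change would then be only √2 × 5 = 7.1 or √2 × 7 = 9.9, which does not agree with the plan's 13.6.

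**The case against.** **Visit may be concealed in practice.** A reader of the protocol might infer that MRI readers know which scan is which. The documents do not say so. Section 8d has electronic images identified by an assigned code, the masking to clinical information could be taken to include scan date, and the two-month rule fixes when a scan is read, not what label the reader sees. With rolling enrolment, coded screening and follow-up scans could arrive mixed, and nothing says the eligibility reader also makes the follow-up read. This stands, so the point is limited to what is not provided for. It does not remove the sequence: the eligibility read is made as a baseline read before follow-up exists, and no other baseline read is planned.

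**The bias is not demonstrated.** Section 4a reports low observer variability and good reproducibility over eight weeks. The endpoint is a change from rest to handgrip within one scan, so a uniform proportional contouring error cancels; only an error that differs between rest and handgrip survives. Five points is nearly two-thirds of 7.8 and would not be a small tendency. All of this stands. Good reproducibility limits random error, however, and does not exclude a directional difference between visits.

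**The plan already has a protected test.** It would be wrong to infer that the primary section contains nothing that cancels a common shift. The unpaired comparison in 7a does so. But section 7c gives it no sample size, and the powered analysis is the exposed one.

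**A re-read might seem to remove the selection effect.** It does so only if reading error is the sole within-person variation, which conflicts with the plan's SD as shown above.

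**Conclusion.** The concern holds in limited form. The plan does not provide for visit masking or random reading order, and as written the selecting read is also the baseline of the paired test on which the sample size rests. Any systematic difference between visits passes into that test undiminished.

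Its size is unknown. The rates of about 11%, 20% and 45% rest on assumed shifts of 2, 3 and 5 points with n=27 and SD 13.6, and they show sensitivity, not expected bias. The regression-to-the-mean figures rest on assumed variance components. The direction is more secure: selecting on a low reading moves the later change upward.

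The placebo comparison in 7a is largely protected against both mechanisms, because reading shifts under drug masking and selection at entry should act alike in the two randomised arms. This is a cheap improvement worth making, and not evidence that the readings will be biased.

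**What to change.** Add to section 4a, MRI analysis: *The screening read is used for eligibility only. Once the follow-up scan is available, both scans of a participant are coded and read in random order by the same reader, masked to drug, visit and the screening result. The endpoint is taken from these reads.*

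In section 7c, state that the two-month limit applies to the eligibility read and to the paired read after follow-up. Pairs can be read as they complete, so the limit still holds for the follow-up scan.

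In section 7a, state that a claim of drug effect rests on the vericiguat-placebo comparison of change already listed there, with the paired analysis as supporting description. The re-read cannot remove regression from scan-to-scan variation, and the placebo contrast is what accounts for it. Section 7c should then report the limited power of that comparison.

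Cost: a few protocol sentences and up to 45 extra baseline reads by the existing reader. No new scan, extra staff or change in planned numbers is needed, and participants already scanned can be included if their images are stored.
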